5 STUDY SUBJECTS VARIABLES AND ANALYSES

5.1 Subject disposition

5.1.1 Subject not randomized

Subjects who discontinued before randomization will be summarized based on the ENR Set and will include:

- Number and percentage of subjects not randomized (based on ‘Was the subject randomized?’ recorded as ‘No’ in the ‘Randomization’ page).
- Primary reason for not being randomized (based on reason for not randomized entered on the ‘Randomization’ page).

All reasons for a subject not being randomized will be listed using the ENR Set.

5.1.2 Study disposition

Study disposition will be summarized based on the ENR Set, presented by randomized treatment group and all enrolled subjects combined, and will include:

- Number of subjects enrolled.
- Number and percentage of subjects randomized (based on non-missing randomization number).
- Number and percentage of subjects treated in the double-blind study period (based on non-missing ‘Treatment start date’ in the ‘Study Double-Blind Treatment Log’ page).
- Number and percentage of subjects who completed the double-blind study period (based on ‘Reason for treatment stop’ entered as ‘Completion as per protocol’ in the ‘Study Double-Blind Treatment Log’ page).
- At the time of interim analysis: number and percentage of subjects ongoing in double-blind treatment at cut-off.
- Number and percentage of subjects treated in the single-blind placebo treatment run-out period (based on a non-missing ‘Treatment start date’ in the ‘Study Single-Blind [Run-Out] Treatment Log’ page).
- Number and percentage of subjects who completed the single-blind placebo treatment run-out period (based on ‘Reason for treatment stop’ entered as ‘Completion as per protocol’ in the ‘Study Single-Blind [Run-Out] Treatment Log’ page).
- At the time of interim analysis: number and percentage of subjects ongoing in single-blind run-out treatment at cut-off.
- Number and percentage of subjects who completed the study (based on ‘Did the subject complete the study?’ recorded as ‘Yes’ in the ‘End of Study Status’ page).

- At the time of interim analysis: number and percentage of subjects ongoing in the study treatment at cut-off.

At the time of interim analysis, study disposition by visit of subjects in the double-blind study period at cut-off will be summarized based on FAS presented by randomized treatment group and all treatment groups combined, and will include:

- Number and percentage of subjects randomized.
- Number and percentage of subjects ongoing between randomization and Week 14 (Visit 3) and discontinued study between randomization and Week 14 (Visit 3).
- Number and percentage of subjects who completed Week 14 (Visit 3).
- Number and percentage of subjects ongoing between Week 14 (Visit 3) and Week 27 (Visit 4) and discontinued study between Week 14 (Visit 3) and Week 27 (Visit 4).
- Number and percentage of subjects who completed Week 27 (Visit 4).
- Number and percentage of subjects ongoing between Week 27 (Visit 4) and Week 40 (Visit 5) and discontinued study between Week 27 (Visit 4) and Week 40 (Visit 5).
- Number and percentage of subjects who completed Week 40 (Visit 5).

5.1.3 Study and study treatment completion/discontinuation

The following summary will be based on the FAS and presented by treatment group and all treatment groups combined:

- Number and percentage of subjects who prematurely discontinued double-blind study treatment (based on reason for treatment stop entered as ‘Discontinuation’ in the ‘Study Double-Blind Treatment Log’ page).
- Primary reason for premature double-blind study treatment discontinuation (based on reason for treatment discontinuation entered on the ‘Study Double-Blind Treatment Log’ page).

All reasons for premature double-blind study treatment discontinuation will be listed based on the FAS.

The following summary will be based on the FAS and presented by treatment group and all treatment groups combined:

- Number and percentage of subjects who prematurely discontinued from the study (based on non-missing reason for stopping study entered in the ‘End-of-Study Status’ page).
- Primary reason for premature discontinuation from the study (based on reason for stopping study entered in the ‘End-of-Study Status’ page).

All reasons for premature study discontinuation will be listed based on the FAS.

The following summary will be based on the FAS and presented by treatment group and all treatment groups combined:

- Number and percentage of subjects who prematurely discontinued single-blind placebo treatment in the run-out period (based on reason for treatment stop entered as ‘Discontinuation’ in the ‘Study Single-Blind [Run-Out] Treatment Log’ page).
- Primary reason for premature single-blind placebo treatment discontinuation in the run-out period (based on reason for treatment discontinuation entered on the ‘Study Single-Blind [Run-Out] Treatment Log’ page).

All reasons for premature single-blind placebo treatment discontinuation in the run-out period will be listed based on the FAS.

Time from randomization to study discontinuation will be summarized by treatment group using Kaplan-Meier plots in the FAS. For subjects who do not complete the study at the time of the interim analysis, time to study discontinuation will be censored at the cut-off date.

5.1.4 Study enrollment

The number and percentage of subjects enrolled as well as subjects enrolled but not randomized will be displayed by country and site based on the ENR Set.

The number and percentage of subjects randomized will be displayed by country and site based on the FAS by treatment group and all treatment groups combined.

The randomization scheme and codes will be listed for randomized subjects only using the FAS.

5.2 Protocol deviations

The FAS will be used for the summary of PDs.

All PDs and important PDs will be summarized in separate tables as per pre-specified category (i.e., selection criteria, IMP, study conduct/procedure, forbidden medication, withdrawal criteria and other) by treatment group and all treatment groups combined. In addition, the same summary of all PDs and important PDs will only be provided separately for PDs related to COVID-19.

A subject may have more than one protocol deviation in a given category, but the subject will be counted only once per protocol deviation category.

A listing of PDs will be provided using the FAS. PDs related to COVID-19 will be flagged in the listing.

5.3 Subject characteristics

Unless noted otherwise, summaries and listings described in this section will be based on the FAS.

Summary tables will be produced by treatment group and all treatment groups combined. Data will be presented individually by subject in the listings.

5.3.1 Demographics and baseline characteristics

Demographic data at screening of the respective confirmatory study (ID-078A301 or ID-078A302) including age, sex, race, ethnicity, height, weight, BMI and region (US, other) will be summarized and listed using the ENR Set and using the FAS.

The number and percentage of subjects randomized in each age category (< 18, 18 – < 65, 65 – < 75, 75 – < 85, 65 – < 85, ≥ 85 years at screening of confirmatory study), in each BMI category (< 25, 25–30, > 30 kg/m² at screening of confirmatory study), and in each region (US, other) will be further summarized using the ENR Set and using the FAS.

The number of subjects treated in each age category (< 18, 18 – < 65, 65 – < 85 and ≥ 85 years at screening of confirmatory study) by sex will be summarized based on the SS.

5.3.2 Baseline disease characteristics

Baseline disease characteristics will come from baseline disease characteristics of the confirmatory study and include: dissatisfaction with sleep quantity or quality (Y/N), difficulty initiating sleep (Y/N), difficulty maintaining sleep characterized by frequent awakenings or problems returning to sleep after awakenings (Y/N), early morning awakening with inability to return to sleep (Y/N) and sleep disturbance causing significant distress or impairment in social, occupational, educational, academic, behavioral, or other important areas of functioning (Y/N).

These baseline disease characteristics, including the time since insomnia diagnosis (in years) at randomization of ID-078A301 or ID-078A302, will be listed and summarized.

An incomplete (day or month missing) or missing insomnia diagnosis date will be imputed using the 15th day of the month (in case only the day is missing) or 1 July (in case day and month are missing).

In the event that the insomnia diagnosis imputed date is after the randomization date of the confirmatory study, then the randomization date of the confirmatory study –1 day will be used as insomnia diagnosis date.

5.3.3 Previous and concomitant diseases

Relevant medical history and current medical conditions will come from the respective confirmatory study (ID-078A301 or ID-078A302) and are coded using MedDRA terminology.

Any disease or diagnosis is defined as previous if ‘Ongoing at informed consent signed’ is answered as ‘No’ in the eCRF of confirmatory studies or extension study.

Medical history at screening of the confirmatory study (i.e., those procedures or diagnoses reported at screening of the respective confirmatory study or those recorded as ‘not ongoing’ in the eCRF at the signing of the informed consent of the extension study) and current medical conditions (i.e., those conditions recorded as ‘ongoing’ in the eCRF at the signing of the informed consent of the extension study), excluding insomnia-related conditions and symptoms, will be summarized separately and listed.

Summaries will be presented for each treatment group by primary SOC and PT.

Medical history will be sorted by SOC and PT within each SOC by descending frequency based on all treatment groups combined.

The MedDRA version used for reporting will be specified in the footnote of the applicable output.

5.3.4 Concomitant therapy

Therapies collected will be coded using the WHO Drug Global reference dictionary that employs the WHO ATC classification system. The WHO Drug Global version used for reporting will be specified in the footnote of the applicable output.

Study concomitant therapies are any treatments that are either ongoing at the date the informed consent of the extension study was signed or initiated during the time from the date the informed consent of the extension study was signed up to EOS. The use of all study-concomitant therapies (including contraceptives and traditional and alternative medicines, e.g., plant-, animal-, or mineral-based medicines) is to be recorded in the ‘Concomitant Medication’ page.

Double-blind study treatment concomitant therapies (a subset of study-concomitant therapies) are any treatments that are either ongoing at the start of double-blind study treatment or initiated during the double-blind study period until 1 day after the last dose of double-blind study treatment.

The number and percentage of subjects having taken at least one concomitant therapy will be summarized by ATC classification level 4 (or next highest available level) and individual preferred name within each ATC classification based on the SS.

Concomitant therapy will be sorted by ATC class and preferred name within each ATC class by descending frequency based on all treatment groups combined.

Summary tables will be provided for study concomitant and double-blind study treatment-concomitant therapies separately. An additional summary table will be provided for double-blind study treatment concomitant therapies at baseline (i.e., therapy started on, or is ongoing at the double-blind study treatment start date). All concomitant therapies will be listed using the SS. The period (double-blind, run-out, Section 11.2) for which the concomitant therapy started will be displayed in the listing and those related to an adverse event (AE) will be flagged.

An incomplete (day or month missing) or missing concomitant therapy date will be imputed as described in Table 1. The 'lower limit' and 'upper limit' refer to the earliest and latest possible dates, respectively. As an example: if concomitant therapy start date is MAR2017 (day missing), the lower limit is 01MAR2017 and the upper limit is 31MAR2017; if concomitant therapy start date is 2017 (day and month missing), the lower limit is 01JAN2017 and the upper limit is 31DEC2017.

Table 1 Imputation rules for an incomplete or missing concomitant therapy date

Field	Incomplete date	Missing date
Concomitant therapy end date	The upper limit.	No imputation; the therapy is considered as ongoing.
Concomitant therapy start date	
The rules below apply in the order presented:
 
 1. For concomitant therapy reported as ongoing from the confirmatory study, the lower limit is used. 2. If the (imputed) concomitant therapy end date is on or after the start of double-blind study treatment, and if the double-blind study treatment start falls within the upper and lower limits (inclusive), the double-blind study treatment start date is used. 3. If the concomitant therapy resolution date is missing, and if the double-blind study treatment start falls within the upper and lower limits (inclusive), the double-blind study treatment start date is used. 4. In all the other cases, the lower limit is used. 	Whichever is the earlier of the concomitant therapy end date or double-blind study treatment start date*.

* If a concomitant therapy is reported as ongoing (from confirmatory study) and if the onset date is missing then the double-blind study start date of the confirmatory study is used.

The purpose of imputing concomitant therapy dates is only to assign a concomitant therapy to a specific treatment phase for the summary tables and listings. However, only the actual dates as reported in the eCRF will be listed. No imputed date is considered in the medical evaluation of a concomitant therapy or an individual AE.

5.4 Study treatment exposure and compliance

Unless noted otherwise, summaries and listings described in this section will be based on the SS.

5.4.1 Study treatment exposure

The duration of double-blind study treatment, and single-blind placebo run-out treatment (including categories: ≤ 4 , $> 4-8$, $> 8-12$, $> 12-16$, $> 16-20$, $> 20-24$, $> 24-28$, $> 28-32$, $> 32-36$, $> 36-40$, > 40 weeks for double-blind study treatment; and 0, 1, 2, 3, 4, 5, 6, 7, 8, 9, ≥ 10 days for single-blind placebo run-out treatment) and duration of double-blind study treatment in subject-years will be summarized for the extension study. The definition of a year is 365.25 days.

The duration of treatment (in days) is defined as the difference between the respective (double-blind/run-out) treatment end date and the respective (double-blind/run-out) treatment start date plus one day. This calculation ignores periods of treatment interruption. Summary for run-out will be based on the TWS.

Additionally, the duration of double-blind study treatment in the confirmatory and extension study is calculated as double-blind study treatment end date of the extension study – double-blind study treatment start date of the confirmatory study + 1 day (including categories: ≤ 12 , $> 12-16$, $> 16-20$, $> 20-24$, $> 24-28$, $> 28-32$, $> 32-36$, $> 36-40$, $> 40-44$, $> 44-48$, $> 48-52$, > 52 weeks for double-blind study treatment in the confirmatory and extension study) and duration in subject-years will be summarized. Interruptions between studies including the run-out period will be ignored. This analysis excludes the subjects who switched from placebo to 25 mg.

The calculation of study treatment duration at the time of an interim analysis will be slightly modified: for subjects who are still on study treatment at the interim cut-off date, this date will be used instead of the double-blind study treatment end date of the extension study. This also means that subjects who complete study treatment after the interim cut-off date will be considered as ‘study treatment ongoing ‘ for the interim report.

Time from first dose of double-blind treatment to treatment discontinuation will be summarized using Kaplan-Meier plots in the SS. For subjects who did not complete the treatment at the time of the interim analysis, time to treatment discontinuation will be censored at the cut-off date.

The duration of treatment along with reason for treatment stop will be listed.

5.4.2 Study treatment compliance

Study treatment compliance will be assessed through study treatment accountability.

The following formula will be used to calculate compliance for both the double-blind study period and the run-out period:

Study treatment compliance (%) = $([\text{number of tablets dispensed} - \text{number of tablets returned}^*] / [\text{treatment duration} - \text{total duration of treatment interruptions}]) \times 100$

* If a subject did not return his/her wallet (e.g., the wallet is lost), the study treatment compliance will not be calculated and the compliance for the period will be set to missing.

Treatment duration and total duration of treatment interruptions in the double-blind or run-out period are calculated using the dedicated eCRF page ‘Study Treatment Log’ as follows:

- Treatment duration (days) = date of last drug intake of double-blind study treatment (run-out single-blind placebo treatment) – date of first drug intake of double-blind study treatment (run-out single-blind placebo treatment) + 1 day.
- Total duration of treatment interruptions (days) is the sum of all treatment interruption durations. A treatment interruption duration = date restarted double-blind study treatment (run-out single-blind placebo treatment) – end date of double-blind study treatment (run-out single-blind placebo treatment) due to an interruption – 1 day. For example, a subject stopped his treatment on 19MAR2019 and started again on 23MAR2019, as the treatment is taken on the start and end date the calculation will be 23MAR2019 – 19MAR2019 – 1 day = 3 days of interruption. Should the subject interrupt the treatment again for 7 days, the total duration of interruptions will be 10 days. In case of a treatment interruption duration of 0 days, the interruption will be counted but the duration of 0 days will not be included in the summary for the duration of treatment interruption. For subjects who complete the study treatment for a given study period but end on an interruption before continuing study treatment in the next study period, the start date of the next study period is used as the date of restarted study treatment of the given study period. E.g., if a subject completed double-blind study treatment with an interruption on 23JUN2019 and then started the treatment withdrawal period on 26JUN2019, the duration of that treatment interruption will be (26JUN2019 – 23JUN2019) – 1 day = 2 days.

The calculation of study treatment duration and total duration of treatment interruptions at the time of an interim analysis will be slightly modified: for subjects who are still on study treatment at the interim cut-off date, this date will be used instead of the last drug intake of double-blind study treatment (run-out single-blind placebo treatment). For subjects who have an ongoing treatment interruption at the interim cut-off date, the interim cut-off date will be used instead of the date restarted double-blind study treatment (run-out single-blind placebo treatment). Subjects who complete study treatment after the interim cut-off date will be considered as ‘study treatment ongoing’ for the interim report.

The percentage of days treated is defined as follows:

- Percentage of days treated: $100 \times (\text{treatment duration} - \text{total duration of treatment interruptions}) / \text{treatment duration}$.

Study treatment compliance (including categories 0%, > 0% – < 50%, 50% – < 70%, 70% – < 80%, 80% – < 90%, 90% – < 100%, 100%, > 100%), number of treatment interruptions per subject by category (0, 1, 2, 3, 4, > 4 interruptions), duration of treatment interruptions and percentage of days treated (including categories 0%, > 0% – < 50%, 50% – < 70%,

70% – < 80%, 80% – < 90%, 90% – < 100%, 100%) will be summarized for the double-blind and run-out period, separately. The summaries of the run-out period will be based on the TWS.

The number and percentage of subjects who have treatment interruptions, and the corresponding reasons will be tabulated.

Study treatment compliance, dispensing and accountability data will be listed.

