11 GENERAL DEFINITIONS AND DERIVATIONS

11.1 Treatment start and end dates

Unless noted otherwise, treatment start and end dates mentioned throughout this document are in reference to the treatment received in the extension study.

Double-blind study treatment start or end date is the earliest or latest, respectively, date of dose intake recorded on the 'Study Double-Blind Treatment Log' page. Double-blind study treatment start or end date of the confirmatory study is the earliest or latest, respectively, date of dose intake recorded on the 'Study Double-Blind Treatment Log' page of either study ID-078A301 or study ID-078A302.

Run-out single-blind placebo treatment start and end date is the earliest and latest date of dose intake recorded on the 'Study Single-Blind (Run-Out) Treatment Log' page.

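### SAP 5.4.2 subtracts the gap before run-out from a treatment duration that ended before the gap, so compliance is overstated for subjects who end double-blind treatment on an interruption

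*SAP*

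**What the plan says.** SAP Section 5.4.2 defines compliance as tablets dispensed minus tablets returned, divided by treatment duration minus total interruptions, times 100. Four of its rules matter here.

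- **Duration ends at the last dose:** "Treatment duration (days) = date of last drug intake of double-blind study treatment", minus the date of first intake, plus 1 day. Section 11.1 agrees: "Double-blind study treatment start or end date is the earliest or latest, respectively, date of dose intake recorded on the" double-blind treatment log.
- **All interruptions are subtracted:** "Total duration of treatment interruptions (days) is the sum of all treatment interruption durations". Nothing excludes an interruption that begins after the last intake.
- **The stop date is a dosing day:** each interruption is restart date minus stop date minus 1 day, because "as the treatment is taken on the start and end date the calculation will be" made that way.
- **Terminal interruption:** for a subject who completes a period but ends it on an interruption, "the start date of the next study period is used as the date of restarted study treatment of the given study period". The worked example has a stop on 23JUN2019 and run-out starting on 26JUN2019, giving a 2-day interruption.

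Percentage of days treated, also in 5.4.2, is duration minus interruptions, divided by duration. The compliance summary has separate categories for 90% to <100%, 100% and >100%.

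**The concern.** The terminal interruption lies after the date on which treatment duration stops. Subtracting it removes days that the duration never contained, so the compliance denominator is too small by the length of the gap and the percentage is too high.

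Three things follow for the table:

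- A subject who took every tablet up to the last double-blind intake is reported above 100%. A reader would normally take that category to mean surplus or unaccounted tablets.
- A subject who missed as many tablets as there are gap days is reported as exactly 100%.
- A subject just below a category boundary can move up one category.

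No planned test, model or analysis set uses compliance, so the stake is the accuracy of a descriptive summary.

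**Working it through.** **Inputs.** Definitions come from SAP 5.4.2 and 11.1. The 40-week double-blind phase (280 days) comes from SAP Section 2. One tablet per day is assumed, as dividing tablets by days implies. The SAP example gives no first-dose date; 19SEP2018 is assumed, so that duration D = 278 at a last intake on 23JUN2019.

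**The plan's own figures.** Interruption = restart − stop − 1.
- 23MAR2019 − 19MAR2019 − 1 = 3 days; with a further 7 days, 10 days in total. Reproduced.
- 26JUN2019 − 23JUN2019 − 1 = 2 days. Reproduced. The two days are 24 and 25 June, both after the last intake.

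**Control: an interruption inside the duration.** A 3-day gap within 280 days, all other doses taken: 277/(280 − 3) = 100%. The formula is sound for interior gaps.

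**Terminal gap g, no dose missed between first and last intake.**
- As written: compliance = D/(D − g); days treated = (D − g)/D.
- With the duration extended to run-out start minus 1 day: duration = D + g; compliance = D/(D + g − g) = 100%; days treated = D/(D + g).

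| D | g | Compliance as written | Compliance corrected | Days treated as written | Days treated corrected |
|---|---|---|---|---|---|
| 278 | 2 | 278/276 = 100.72% | 100% | 276/278 = 99.28% | 278/280 = 99.29% |
| 280 | 1 | 280/279 = 100.36% | 100% | 279/280 = 99.64% | 280/281 = 99.64% |
| 280 | 2 | 280/278 = 100.72% | 100% | 278/280 = 99.29% | 280/282 = 99.29% |
| 280 | 3 | 280/277 = 101.08% | 100% | 277/280 = 98.93% | 280/283 = 98.94% |
| 280 | 7 | 280/273 = 102.56% | 100% | 273/280 = 97.50% | 280/287 = 97.56% |

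**Missed tablets hidden (D = 280).**
- g = 2, 1 missed: 279/278 = 100.36%, against 279/280 = 99.64%.
- g = 2, 2 missed: 278/278 = 100%, against 278/280 = 99.29%.
- g = 7, 7 missed: 273/273 = 100%, against 273/280 = 97.50%.

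**Category boundary (D = 280, g = 7).** The 80% line is 0.8 × 273 = 218.4 tablets as written and 0.8 × 280 = 224 tablets corrected. Subjects with 219 to 223 tablets are therefore placed in 80% to <90% instead of 70% to <80%.

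**Comparison with the interim rule.** For a subject still on treatment at the interim cut-off, 5.4.2 says of the cut-off that "this date will be used instead of the last drug intake of double-blind study treatment", and an ongoing interruption also ends at the cut-off. If a subject in an ongoing interruption counts as still on treatment, the gap lies inside the duration. With D = 278 and a cut-off 3 days after the last dose, the duration is 281, the interruption 2 and the denominator 279, so 278/279 = 99.64%. It falls one day short of 100% because the cut-off is treated as a restart day. The terminal rule gives a denominator of 276 for the same 3-day interval.

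**The case against.** The strongest reply is about weight. Compliance is descriptive and feeds no model, analysis set or safety rule. Run-out is planned to start on the evening of Visit 5, so any gap is a departure from schedule. The SAP illustrates only a 2-day gap, worth about 0.7 points. Interruption durations are summarised and accountability is listed, so affected subjects could be traced. All of this stands and limits the impact, but it does not make the calculated value right.

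It can also be said that Section 11.2 already extends the double-blind study period to run-out start minus 1 day for these subjects. It does, but the compliance formula uses intake dates, so the extension never reaches the denominator.

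Other objections have partial force:

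- The subject took nothing on the gap days, so describing no dose as missed needs care. Here it means none missed between first and last intake; the compliance formula itself leaves interruption days out of account.
- Percentage of days treated is hardly affected, as the table shows.
- The interim rule has its own one-day quirk, and the SAP does not say whether a subject in an ongoing interruption is still on treatment. It is a useful contrast, not a model to copy.
- The >100% category can also arise from unreturned tablets, and the SAP gives it no stated meaning.
- Extending the duration in 5.4.2 alone gives these subjects a different duration from the one in 5.4.1. That is a real cost and should be stated in the SAP.

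**Conclusion.** The concern holds. As written, the terminal-interruption rule overstates compliance by the factor D/(D − g) for every subject who completes double-blind treatment but ends on an interruption of at least 1 day. It puts those who missed no dose up to their last intake in >100% instead of 100%. At 280 days the excess is 0.36 to 2.56 points for gaps of 1 to 7 days. Percentage of days treated mixes the same two time bases, but changes by at most 0.06 points in the cases computed.

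This rests on one tablet per day and on assumed durations of 278 or 280 days; gaps other than 2 days are illustrative. The documents do not say how many subjects are affected. The impact is low and confined to descriptive tables, but the correction should be made.

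**What to change.** In SAP 5.4.2 only, add that for subjects who complete double-blind treatment but end on an interruption before run-out, treatment duration for compliance and for percentage of days treated ends at run-out start minus 1 day. In the SAP example the duration becomes 280, compliance 278/(280 − 2) = 100% and days treated 278/280 = 99.29%.

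The alternative is not to subtract the terminal gap at all. That also gives 278/278 = 100% compliance, but makes days treated 278/278 = 100%, which is a different measure. The SAP should choose one and say so.

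Leave the exposure duration in 5.4.1 and the study periods in 11.2 as they are, and note that the 5.4.2 duration differs from 5.4.1 for these subjects. The cost is one sentence and one derivation, with no new data and no change to exposure or safety tables.

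### At an interim, the SAP's rule for a treatment interruption still ongoing at the cut-off counts one untreated day too few

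*SAP*

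**What the plan says.** SAP 5.4.2 (Study treatment compliance) sets the general rule: "A treatment interruption duration = date restarted double-blind study treatment" minus the date treatment stopped for the interruption, minus 1 day. The reason comes with the first example, in which "a subject stopped his treatment on 19MAR2019 and started again on 23MAR2019": "as the treatment is taken on the start and end date", only the days in between count, and the result is 3 days. A second example, for a subject whose double-blind treatment ends on an interruption, applies the same formula with the start of the next period as the restart date and gives 2 days.

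The interim paragraph of 5.4.2 makes two substitutions:

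- Treatment duration: "for subjects who are still on study treatment at the interim cut-off date, this date will be used instead of the last drug intake".
- Interruption length, where the interruption is ongoing at the cut-off: "the interim cut-off date will be used instead of the date restarted double-blind study treatment".

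The paragraph does not mention the 1-day subtraction. SAP section 10 says that every analysis in the SAP will be carried out for the interim, and that assessments made on the cut-off date itself are included.

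**The concern.** The subtraction of 1 day is correct only if both endpoints are dosing days. A subject whose interruption is ongoing at the cut-off has, by definition, not restarted by then, so the cut-off date is an untreated day. Putting it in the restart position and still subtracting 1 day drops that day from the interruption.

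Three interim summaries use the interruption total: duration of interruptions, percentage of days treated (where it is subtracted in the numerator) and compliance (where it is subtracted in the denominator). The last two are also tabulated in categories with boundaries at 90% and 100%, so a one-day error can move a subject to another category.

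**Working it through.** **Inputs, all from SAP 5.4.2.** S is the last dosing day before the interruption, R the restart date, C the interim cut-off date and F the first dosing day.

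- Completed interruption = R − S − 1.
- Ongoing interruption at an interim, as written = C − S − 1.
- Treatment duration = last intake − F + 1, with C replacing last intake at an interim for subjects still on study treatment.
- Percentage of days treated = 100 × (duration − interruptions) / duration.
- Compliance = 100 × (tablets dispensed − tablets returned) / (duration − interruptions).

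**Step 1: reproduce the SAP's examples.** 19 March to 23 March 2019: 23 − 19 − 1 = 3 days (20, 21 and 22 March). 23 June to 26 June 2019: 26 − 23 − 1 = 2 days (24 and 25 June). Adding the further 7-day interruption in the first example gives 3 + 7 = 10. All agree with the SAP.

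**Step 2: count the ongoing case.** The untreated days are S + 1 to C, which number C − S. The rule gives C − S − 1, always one fewer. With k untreated days up to and including the cut-off:

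| k | Rule gives |
|---|---|
| 1 | 0 |
| 2 | 1 |
| 4 | 3 |
| 10 | 9 |

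For k = 1, section 5.4.2 still counts the interruption but leaves its zero duration out of the duration summary.

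**Step 3: check for consistency within the SAP.** Take an illustrative record with first dose on Day 1, stop on Day 116 and cut-off on Day 120. The untreated days are 117 to 120, which is 4; the rule gives 120 − 116 − 1 = 3. If the subject then restarts on Day 121, the final analysis gives 121 − 116 − 1 = 4. All four of those days had passed by the cut-off, yet the interim reports three.

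**Step 4: carry it through, with duration running to the cut-off (120 days).**

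- Percentage of days treated: (120 − 3)/120 = 97.5% as written; (120 − 4)/120 = 96.7% when counted correctly.
- Compliance, if exactly one tablet per treated day is accounted for (116 tablets): 116/117 = 99.1% as written; 116/116 = 100% when counted correctly.
- A category change in days treated, with an assumed duration of 98 days and k = 10: (98 − 9)/98 = 90.8% as written; (98 − 10)/98 = 89.8% when counted correctly.

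**Step 5: the other reading of duration.** If an interrupted subject is not regarded as still on study treatment, duration ends at last intake (116 days). The rule then gives (116 − 3)/116 = 97.4% days treated and 116/113 = 102.7% compliance, although drug was taken on all 116 days. This subtracts untreated days that were never in the duration, so it is not a workable reading. It does show that the direction of the percentage errors depends on a point the SAP leaves open.

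**The case against.** The count itself is hard to dispute: nothing elsewhere in the SAP restores the lost day. The case on the other side concerns reach and consequence, and much of it stands.

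- A reader might infer that every subject off drug at the cut-off is affected. The text does not support that. Subjects who permanently discontinued earlier are off drug too, but have no ongoing interruption, so the substitution does not apply to them.
- A reader might infer that percentage of days treated is certainly inflated. That follows only if interrupted subjects count as still on study treatment. The SAP handles the two groups in separate sentences and does not link them. Step 5 shows why running duration to the cut-off is the sensible reading, but it remains an inference.
- A reader might infer that a fully compliant subject will show compliance below 100%. That requires all tablets to be accounted for at the cut-off. A subject in mid-interruption may still hold a wallet. If it is treated as not returned, section 5.4.2 sets compliance to missing; if its tablets count as dispensed, the numerator is too high.
- The error is small. In the Day 116/Day 120 example both percentages of days treated fall in the same reporting category. Exposure is unaffected because section 5.4.1 ignores interruptions, and the interim outputs concerned are descriptive.

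It could also be argued that a programmer would drop the subtraction unprompted. The paragraph replaces one date and changes nothing else, so a literal implementation keeps it.

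**Conclusion.** Wrong as written, minor, and confined to interim analyses. For each subject with an interruption ongoing at an interim cut-off, the interruption is understated by exactly one day. This holds whichever way treatment duration is read and needs no outside figure.

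The effects on the percentages are conditional. If duration runs to the cut-off, the untreated cut-off day stays among the days treated and in the compliance denominator. The compliance effect becomes visible only where every tablet is accounted for. The documents do not say how many subjects will have an ongoing interruption at the cut-off, so the effect on the summary tables cannot be sized beyond one day per affected subject. Completed interruptions and the final analysis are correct as they stand, and no efficacy or safety conclusion depends on this.

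**What to change.** In the interim paragraph of SAP 5.4.2, make two statements for subjects with an interruption ongoing at the cut-off, in the double-blind or the run-out period:

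1. Interruption duration = interim cut-off date − stop date, without subtracting 1 day.
2. Treatment duration for these subjects runs to the interim cut-off date inclusive.

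Both are needed. Correcting the interruption alone, with duration still ending at last intake, would give (116 − 4)/116 = 96.6% days treated in the example, further from the truth than the present rule. Writing the formula directly is also cleaner than a notional restart on the day after the cut-off, since section 10 limits the interim analysis datasets to data up to the cut-off.

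The cost is a sentence or two in the SAP and a small change to the derivation code. No data collection or clinical procedure changes.
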